Abstract	Bile acid malabsorption (BAM), also known as bile acid diarrhea (BAD), is a condition characterized by excessive biosynthesis of bile acids or inability to reabsorb sufficient bile acids in the terminal ileum (1,2). This results in unabsorbed bile acids in the colon leading to increased colonic secretion of fluid, thereby causing diarrhea. BAM/BAD contributes to symptoms in a subset of individuals with Irritable bowel syndrome (IBS), which is the most common lower gastrointestinal (GI) disorder that affects 11% of adults (3). Currently, IBS and subgroups diarrhea-predominant IBS (IBS-D), and IBS-constipation (IBS-C), are defined by symptoms alone. Apart from central hypervigilance and psychological disturbances in IBS (4), 48% of IBS-D patients have accelerated colonic transit, 21% have increased rectal sensation (5), and 25-33% of IBS-D patients have abnormal bile acid (BA) synthesis or excretion (6). Aldafermin (NGM282) is an analog of fibroblast growth factor 19 (FGF19), a potent inhibitor of bile acid (BA) synthesis in animals and humans.
Hypothesis	Aldafermin reduces bile acid synthesis and fecal excretion of bile acids and normalizes symptoms of colonic dysfunction in BAM/BAD with increased fecal BA excretion.
Specific Aim	This single-center, randomized, double-blind, placebo-controlled study is designed to compare effects of aldafermin, 1 mg and placebo SQ daily, on bowel functions, hepatic synthesis and fecal excretion of bile acids in patients with diarrhea associated with bile acid malabsorption (BAM).
Number of Subjects	Approximately 36 patients with laboratory confirmed BAM will be enrolled.
Study Duration	The study includes a maximum 28-day prescreen period and a 28-day treatment period for a maximum duration of 56 days.

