Statistical Methods	
Sample size: 30 patients, 15 in placebo group, 15 in aldafermin treatment group.
 
Statistical analyses: Effects of treatment will be compared using Intent-to-Treat principles using ANCOVA with BMI, gender and baseline fasting C4 as covariates. Adverse events (AEs) will be listed and summarized by system organ class and preferred term, as well as according to severity and causality/relationship to study treatment. Observed values for clinical laboratory tests, vital signs and safety 12-lead ECGs will be summarized by treatment. Observed values will be classified as normal, abnormality that is not clinically significant, and clinically significant abnormality by treatment. Results of other safety assessments will be listed and summarized as appropriate.
 
Statistical power: Based on the prior open-label study, the proposed sample size of 15 per group has ~80% power (2-sided $\alpha=0.05$) to detect clinically relevant effect sizes in serum C4 and stool consistency.
 
Anticipated results and significance: Aldafermin will reduce serum C4 and percent

[figure not shown]
	fecal primary bile acids in a random stool sample; preliminary data will be obtained regarding efficacy on stool frequency and stool consistency in BAM/BAD with high BA excretion.
--	---

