1.2 Experimental Therapies for BAM/BAD

A prior open-label study of the BA sequestrant, Colesevelam, in 12 patients with IBS-D and high fecal bile acid excretion demonstrated biological relevance of increased fecal BA excretion (12).

[figure not shown]
Effects of colesevelam on sequestration of bile acid (methanol extraction of stool released the bile acids showing that increased amounts were bound) and reduced stool form. Colesevelam improved stool consistency, sequestering and inactivating BA (shown by increased BA in stool after methanol extraction).

[figure not shown]
On the other hand, a randomized, controlled trial with colesevelam, 1.875g bid, of 4 weeks' duration (13) did not significantly impact symptoms (stool frequency and consistency) although there was evidence of biological efficacy, with significant changes in sequestered fecal total BA excretion ($P < .001$) and serum levels of C4 and FGF19 (both $P < .001$), and with a mean increase in fecal level of deoxycholic acid (10%; $P = 0.07$) compared to placebo.

Effects of colesevelam on stool frequency and consistency in patients with IBS-D and BAD in randomized controlled study

The FXR agonist, tropifexor, has been tested in a small multicenter study, randomized crossover study in patients with primary BAM/BAD (14). Tropifexor 60 μ g once daily had acceptable safety and tolerability. Effects on changes in FGF19 and C4 showed effective target engagement; however, higher doses may be required to observe stool frequency changes. On the other hand, slowing of ascending colon emptying suggests therapeutic potential of tropifexor in patients with primary BAM/BAD.

Effect of tropifexor on gastrointestinal transit in the single center sub-study. A, Ascending colon emptying $T_{1/2}$ ($n = 8$) on Day 12 of each phase. Left panel shows a statistically significant ($p = 0.036$) slowing of the mean ascending colon emptying with tropifexor vs. placebo on Day 12. Right panel shows the ascending colonic $T_{1/2}$ in individual patients.

6-ethyl CDCA or **obeticholic acid** is another FXR agonist that has also been tested for idiopathic BAM/BAD (15). Obeticholic acid stimulates FGF-19, reduces bile acid synthesis and produces clinical benefits in bile acid diarrhea.

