2.2 Study Endpoints

Primary Endpoints

1. Change in fasting serum C4 levels from Baseline to Day 28
2. Change in stool consistency based on the Bristol Stool Form Scale, BSFS from Baseline to Day 28

Secondary Endpoints

1. Stool consistency based on Bristol Stool Form Scale, BSFS
 - a. Absolute change in stool consistency from baseline to Day 14 and Day 28 of treatment.
 - b. Average daily stool consistency score at Day 14 and Day 28 of treatment

[figure not shown]
2. Maximum abdominal pain score rated by patient using an 11-point scale, 0 to 10 inclusive with 0 as none and 10 as worst imaginable abdominal pain.
3. Absolute change in abdominal pain from baseline to Day 14 and Day 28 of treatment.
4. Number of bowel movements per week
5. Change in total fecal bile acid concentration between baseline and Day 28.
6. Proportion of fecal secretory (CDCA + DCA) bile acid as measured in a single, random stool sample by a validated laboratory assay.
7. Proportion of fecal primary (CDCA + CA) bile acid as measured in a single, random stool sample by a validated laboratory assay.
8. Total fecal bile acid concentration in a single, random stool sample as measured by a validated laboratory assay.
9. Total aldafermin concentration in serum as measured by a validated laboratory assay

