7. STATISTICAL CONSIDERATIONS

7.1 Sample Size and Statistical Power

Based on the endpoints of interest in patients with bile acid diarrhea [12], the proposed sample sizes have ~80% power (2-sided $\alpha=0.05$) to detect clinically relevant effect sizes in serum C4 and stool form (expressed as detectable difference $[\Delta]$ in 2 groups:

Table 1: Detectable differences based on 80% power in patients with BAD *not* receiving BA sequestrant

Response	Mean (SD)	Detectable Δ absolute with n=9 per group
Serum C4 ng/mL	72.3 (45.6)	64.1 (1.34*SD or 89 % of baseline mean)
% fecal primary BA	15.7 (20)	28.1 (1.79*SD or 179 % of baseline mean)
# BMs per week	15.1 (7.1)	10.0 (1.41*SD or 66 % of baseline mean)
Stool form (BSFS 1-7 scale)	4.4 (1.12)	1.58 (1.41*SD or 35.9 % of baseline mean)

Based on our previous open-label study demonstrating effects of a bile acid sequestrant (colesevelam) as a typical baseline results for patients on bile acid sequestrants:

Table 2: Detectable differences based on 80% power in patients with BAD receiving BA sequestrant

Response	Mean (SD)	Detectable Δ absolute with n=6 per group
Serum C4 ng/mL	112.5 (50.6)	90.8 (1.79*SD or 80.7 % of baseline mean)
% fecal primary BA	2.7 (7.4)	13.3 (1.80*SD or 492% of baseline mean)
# BMs per week	21.7 (7.1)	12.75 (1.80*SD or 58.8 % of baseline mean)
Stool form (BSFS 1-7 scale)	4.6 (0.6)	1.08 (1.80*SD or 23.5% of baseline mean)

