7.2 Statistical Analysis

Effects of treatment will be compared using Intent-to-Treat principles using ANCOVA with BMI, gender and baseline fasting C4 as covariates. In order to reach 30 subjects, accrual will be set at 36 to replace any volunteer(s) who withdraw prior to taking less than 1 day of dosing. Any Subject who receives more than 1

day of dosing will be consider completed using the Intent-to-Treat analysis.

Primary endpoints are change in fasting serum C4 levels from baseline to Day 28 and change in stool consistency based on Bristol Stool Form Scale, BSFS from baseline to Day 28.

Secondary endpoints are

- Absolute change in stool consistency from baseline to Day 14 and Day 28 of treatment
- Average daily stool consistency score at Day 14 and Day 28 of treatment
- Maximum abdominal pain score rated by patient using an 11-point scale, 0 to 10 inclusive with 0 as none and 10 as worst imaginable pain
- Absolute change in abdominal pain from baseline to Day 14 and Day 28 of treatment
- Number of bowel movements per week
- Change in total fecal bile acid concentration between baseline and Day 28
- Proportion of fecal secretory (CDCA+ DCA) bile acid as measured in a single, random stool sample by a validated laboratory assay.
- Proportion of fecal primary (CDCA + CA) bile acid as measured in a single, random stool sample by a validated laboratory assay.
- Total fecal bile acid concentration in a single, random stool sample as measured by a validated laboratory assay.
- Total aldafermin concentration in serum as measured by a validated laboratory assay

Adverse events (AEs) will be listed and summarized by system organ class and preferred term, as well as according to severity and causality/relationship to study treatment.

Observed values for clinical laboratory tests, vital signs and safety 12-lead ECGs will be summarized by treatment. Observed values will be classified as normal, abnormality that is not clinically significant, and clinically significant abnormality by treatment.

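### Two primary endpoints are each powered at the full two-sided 0.05, with no testing order, alpha split or success rule, so the overall error rate and the reading of a split result are left open

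*Combined protocol and SAP*

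**What the plan says.** Two primary endpoints are named consistently in the synopsis (Study Endpoints), section 2.2 and section 7.2. Section 7.2 states: "Primary endpoints are change in fasting serum C4 levels from baseline to Day 28 and change in stool consistency". In section 2.2 one is "Change in fasting serum C4 levels from Baseline to Day 28"; the other is the change in stool consistency on the Bristol Stool Form Scale (BSFS) over the same interval.

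The only significance level in the documents, two-sided 0.05, appears in the power statements. Section 7.1 claims about 80% power "to detect clinically relevant effect sizes in serum C4 and stool form (expressed as detectable difference" and lists differences separately for patients off sequestrant (Table 1, 9 per group) and on sequestrant (Table 2, 6 per group). The synopsis states that "the proposed sample size of 15 per group has ~80% power" for the same two measures, without giving a difference.

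For efficacy, section 7.2 specifies an intent-to-treat ANCOVA with BMI, gender and baseline C4 as covariates, and then lists the endpoints. It gives no test level, order, alpha allocation, multiplicity adjustment or definition of success.

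**The concern.** With two primary tests and no rule connecting them, three readings are open: either endpoint suffices, both are needed, or one leads. They have different error rates and different power, and the plan does not choose between them. The choice could therefore be made once the results are known.

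The case that exposes the gap is a split result, with one endpoint significant and the other not. The protocol's own background makes this plausible. Section 1.2 reports that a randomized colesevelam trial "did not significantly impact symptoms (stool frequency and consistency) although there was evidence of biological efficacy". The same section says of obeticholic acid that it "reduces bile acid synthesis and produces clinical benefits in bile acid diarrhea". A split is therefore possible but not predicted, and its interpretation should be fixed in advance.

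**Working it through.** **Inputs.** Two primary endpoints (section 7.2); two-sided 0.05 for each, 15 per group (synopsis, section 7.1); stratum sizes, SDs and differences from Tables 1 and 2. The documents give no correlation between the two test statistics, so I assume 0 to 1. Power uses the two-sample t test, because no covariate correlations are given for the ANCOVA.

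**1. The plan's own power.** Noncentral t, with noncentrality (Δ/SD)·√(n/2) and 2n − 2 degrees of freedom:

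| Stratum | Endpoint | Δ/SD | Power at 0.05 | Power at 0.025 |
|---|---|---|---|---|
| Off, n=9 | C4 | 64.1/45.6 = 1.406 | 79.9% | 69.3% |
| Off, n=9 | BSFS | 1.58/1.12 = 1.411 | 80.2% | 69.6% |
| On, n=6 | C4 | 90.8/50.6 = 1.794 | 80.0% | 68.1% |
| On, n=6 | BSFS | 1.08/0.6 = 1.80 | 80.2% | 68.4% |

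The stated 80% is reproduced only with the full 0.05 on each endpoint. (Table 1 prints 1.34 SD for C4; the absolute difference of 64.1 corresponds to 1.41 SD and is used here.) At 15 per group, 80% power corresponds to 1.06 SD.

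**2. Either endpoint suffices, no effect on either.** At correlation 0, familywise error is 1 − (1 − 0.05)² = 9.75%. By simulation and the bivariate normal it is about 9.1% at correlation 0.5, about 7.9% at 0.8, and 5% at 1. Counting benefit-direction claims only, 1 − (1 − 0.025)² = 4.94% at correlation 0, about 4.5% at 0.5, 3.9% at 0.8 and 2.5% at 1. Negative correlation can raise this figure to at most 5.0%.

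**3. Either endpoint suffices, C4 truly moves.** Only the BSFS claim can be false, so the error is that of a single test: 5%.

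**4. Both endpoints required.** Error stays at or below 5%. With 80% power each, joint power is 0.80 × 0.80 = 64% at correlation 0, 68% at 0.5 and 73% at 0.8 (simulated).

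**5. Probability of a split at 80% power each.** This is 2 × (0.80 − joint power): 2 × (0.80 − 0.640) = 32%; 2 × (0.80 − 0.685) = 23%; 2 × (0.80 − 0.727) = 15%, at correlations 0, 0.5 and 0.8.

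**6. Probability of a split at the tabulated differences.** Pooling 9 off-sequestrant and 6 on-sequestrant patients per group:
- C4 mean = (9 × 72.3 + 6 × 112.5)/15 = 88.38.
- C4 SD = √{[9(45.6² + 16.08²) + 6(50.6² + 24.12²)]/15} = 51.6.
- The same method gives 0.95 for BSFS.

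At 15 per group:
- C4: 64.1/51.6 = 1.24, power 91%.
- BSFS, Table 1: 1.58/0.95 = 1.66, power 99%.
- BSFS, Table 2: 1.08/0.95 = 1.14, power 85%.

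With the Table 1 BSFS difference, a split occurs in 9–10% of trials. With the Table 2 BSFS difference it is 21%, 16% and 11% at correlations 0, 0.5 and 0.8; at correlation 0 this is 0.907 × 0.148 + 0.093 × 0.852 = 0.213.

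**The case against.** The strongest reply is that this is a small, single-center, investigator-initiated trial; that the two endpoints answer different questions, one a biomarker and one a symptom; and that if each supports only its own claim, the error per claim is already 5%. Whether familywise control is then needed is a matter of judgement. This argument has force, but it describes a rule that the plan does not state. Writing it down would settle how a split is read, though not the familywise rate if one success is called a positive trial.

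A second reply is that the documents already imply an order. The synopsis, under anticipated results, predicts a fall in C4 but describes what will be learned about stool consistency as preliminary. That leans towards C4 as lead endpoint, and it means one cannot safely say that the documents rank the two equally. It is still not a testing rule, and the same synopsis powers both endpoints. The numbering in section 2.2 is only a list; secondary endpoints are numbered in the same way. The hypothesis, "Aldafermin reduces bile acid synthesis and fecal excretion of bile acids and normalizes symptoms of colonic dysfunction", could be read as requiring both, but no joint power is claimed.

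A reader might also infer that the primary result can be chosen freely afterwards. That goes too far: both measures and the Day 28 time point are fixed and stated consistently, so the latitude is confined to two named results.

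**Conclusion.** The gap is real and should be closed, but its size is conditional. A reader might infer that the trial runs at 9.75% type I error. The documents do not support that as a flat statement: it requires an either-endpoint rule that is nowhere stated, no effect on either endpoint, and uncorrelated statistics. It is a ceiling, and drops to 5% if C4 truly responds. A null C4 effect cannot be excluded, however: in the constipation trial in section 1.3, the C4 change with 1 mg versus placebo had P = 0.12.

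Likewise, 32% is the upper end for a split result and assumes 1.06 SD on both endpoints, a difference that no section states. At the tabulated differences the range is about 9–21%. Those differences were set for the strata, so applying them to 15 per group is itself an assumption.

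What does not depend on these assumptions is that the plan as written produces two unadjusted primary tests and no pre-stated reading when they disagree. The missing rule costs either alpha (either-endpoint reading) or power (both-required reading).

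**What to change.** Before unblinding, add one rule to section 7.2 that holds the overall two-sided alpha at 0.05 and says how a split result is read. The sponsor should choose it, since the documents do not show which is intended. No added patients are needed. Two suitable options:

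- **Holm.** Compare the smaller p-value with 0.025 and, if significant, the other with 0.05; each significant endpoint supports only its own claim. At 15 per group and 1.06 SD on both endpoints, power per endpoint falls from 80% to 77%, 76% and 75% (correlation 0, 0.5, 0.8), or to about 70% if the other endpoint has no effect. The chance of at least one supported claim falls from 96%, 92% and 87% to 91%, 85% and 79%.
- **Fixed sequence, C4 then BSFS, each at 0.05.** This suits the plan if the sponsor regards C4 as the lead endpoint. C4 keeps its 80% power. BSFS cannot be claimed if C4 fails, so at 80% power each the chance of a BSFS claim equals the joint power, 64–73%.

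Requiring both endpoints would also control the error, with the joint power shown above as its cost. Section 7.1 and the synopsis power statement should then be restated to match the chosen rule.

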1.3 Aldafermin

Aldafermin (NGM282) is a recombinant protein with 95.4% of its 190 amino acids identical to fibroblast growth factor 19 (FGF19) and with similar binding affinity to FGFR4 and KLB co-receptor on human hepatocytes. The molecule aldafermin mimics the actions of FGF19 on bile acid synthesis by decreasing the gene expression in human hepatocytes of CYP7A1 which is responsible for catalyzing the rate limiting step of cholesterol conversion to bile acids. This has been demonstrated by a rapid and dose-dependent reduction in levels of serum 7-alpha-hydroxy-4-cholesten-3-one (C4), a key intermediate metabolite of CYP7A1-mediated bile acid synthesis in mice and humans (16-18).

This investigator-initiated study will be conducted under an investigator-held IND [REDACTED] with a Letter of Authorization from NGM Biopharmaceuticals, Inc. based upon the existing aldafermin INDs [REDACTED] and [REDACTED]. A prior study of aldafermin (NGM282) was conducted a few years ago in patients with functional constipation under IND [REDACTED].

In this prior study (19), we showed there was a dose related effect of aldafermin on colonic transit in patients with functional constipation, with significant effect on colonic transit (particularly ascending colon emptying) and bowel frequency with the 1mg dose of aldafermin in contrast to the stimulation with the 6 mg dose:

Data LSM (SEM)	Placebo (PLA) n=10	NGM282 1mg, n=10	NGM282 6mg, n=11	P ANOVA	NGM282 1mg vs PLA	NGM282 6mg vs PLA
GE T _{1/2} ,min	132.4 (7.4)	97.8 (7.2)	94.5 (8.1)	0.002	0.003	0.001
CT GC24	2.03 (0.16)	2.35 (0.18)	3.30 (0.29)	< 0.001	0.070	< 0.001
CT GC48	3.36 (0.29)	4.29 (0.22)	4.66 (0.13)	< 0.001	0.001	< 0.001
AC T _{1/2} , h	20.0 (2.9)	16.7 (1.8)	12.2 (1.6)	0.049	0.300	0.015
# BM/week	5.1 (0.5)	8.0 (0.7)	15.1 (2.3)	< 0.001	0.178	< 0.001
Fasting C4 ng/mL	27.7 (7.9)	9.5 (4.3)	2.6 (1.9)	0.89	0.98	0.72
Δ Fasting C4 on Rx minus pre-Rx, ng/mL	5.9 (5.2)	-2.9 (4.0)	-8.3 (2.3)	0.056	0.12	0.018

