4.4 Patient Withdrawal and Replacement

If a patient is pregnant, the patient will be withdrawn from study treatment immediately.

A patient may be withdrawn for any treatment related adverse event or clinically significant findings in clinical labs or other vital signs that are deemed by the investigator to pose an unacceptable risk to the patient. If the study is interrupted due to any of the criteria listed above, the patient may undergo unscheduled assessments to evaluate his/her status. Additional subsequent visits may be required to assess event outcomes.

Study treatment may be discontinued, interrupted or dose reduced for any grade 3 adverse event that is possibly or probably related to study treatment. Study treatment will be discontinued for any grade 4 adverse event that is possibly or probably related to study treatment

Patients may also be discontinued from the study at any time for any of the following reasons:

- Adverse event
- Death
- Lost to follow-up
- Investigator decision
- Pregnancy
- Protocol deviation
- Study terminated by Sponsor
- Withdrawal by subject

A patient may be withdrawn from the study at any time due to the following adverse events based on the known safety profile and mechanism of the drug:

- Dehydration requiring hospitalization
- A laboratory result of total cholesterol and triglycerides $> 2 \times$ ULN
- Allergic reaction requiring hospitalization

A patient may be withdrawn from the study at any time due to the following adverse events:

- A laboratory result of ALT or AST $> 3 \times$ ULN, total direct bilirubin $> 2 \times$ ULN or serum creatine > 2.5 ULN
- Abnormal cardiac findings such as a clinically significant abnormal heart rate or rhythm, left bundle branch block with QRS interval > 110 msec or first-degree AV block with PR interval > 220 msec.

A patient may be withdrawn by the investigator or the sponsor if enrollment in the study is deemed inappropriate, the study plan is violated, or for administrative and/or safety reasons.

A patient may elect to discontinue study participation at any time for any reason without prejudice to his/her

future medical care by the physician or at the institution. The investigator will document the specific reason why consent was withdrawn.

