6.6 Clinical Laboratory Tests

Clinical safety laboratory tests will be performed at the study site at Visit 1 Screen or Visit 2 and Visit 5 End of Study. These tests include the Comprehensive Metabolic Panel, calcium, creatinine, sodium, potassium,

albumin, alkaline phosphatase, total bilirubin, carbon dioxide, chloride, glucose, total protein, BUN, AST, and ALT. Hematology includes a CBC with differential. A lipid panel including total cholesterol, HDL, LDL and triglycerides will be performed. Analysis of the urine will be completed by a standard urine dipstick method with microscopy. The investigator will the laboratory report, document the review, and record any clinically relevant changes as AEs.

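### The group-level safety summary does not use the pre-dose laboratory values the trial collects, so with about 15 patients per arm a moderate shift in mean lipids is estimated imprecisely

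*Combined protocol and SAP*

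**What the plan says.** Section 7.2 gives the group-level plan for laboratory tests, vital signs and ECGs in two sentences: "Observed values for clinical laboratory tests, vital signs and safety 12-lead ECGs will be summarized by treatment", and "Observed values will be classified as normal, abnormality that is not clinically significant, and clinically significant abnormality by treatment". The synopsis repeats both and adds "Results of other safety assessments will be listed and summarized as appropriate", which covers assessments other than these three. The ANCOVA described in 7.2 adjusts for BMI, gender and baseline fasting C4, so it brings in no pre-dose laboratory safety value.

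On data collection, section 6.6 states: "Clinical safety laboratory tests will be performed at the study site at Visit 1 Screen or Visit 2 and Visit 5". The panel includes total cholesterol, HDL, LDL, triglycerides and ALT. Sections 3.2, 3.3 and 3.6 agree with this: one panel before dosing and one at the end of treatment.

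On mechanism, section 1.3 says the drug lowers expression of CYP7A1, the enzyme "responsible for catalyzing the rate limiting step of cholesterol conversion to bile acids". Section 4.4 puts a total cholesterol and triglycerides result in a list of withdrawal events introduced as "based on the known safety profile and mechanism of the drug".

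Baseline does enter the review of individual patients. Sections 6.2 and 6.6 make clinically relevant laboratory changes adverse events, 7.2 summarises adverse events, and section 3.6 asks for a repeat test after a clinically significant change, with pre-study levels as the reference.

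**The concern.** The protocol itself gives a reason to watch lipids, and the schedule supplies a before-and-after pair of panels. The written group-level analysis does not use the pairing. This has two consequences.

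- **Precision.** An arm comparison of observed values carries the full between-patient spread. Where pre-dose and Visit 5 values are well correlated, much of that spread can be removed by adjusting for the pre-dose value.
- **Interpretation of the class table.** The numbered exclusions set no lipid limit, so some patients may enter with abnormal lipids. A patient abnormal at both visits and one who became abnormal on treatment fall in the same Visit 5 cell.

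At stake is how well this small trial can describe a moderate lipid effect. The primary endpoints are not affected.

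**Working it through.** **The plan's own figures.** The documents give no precision or power figure for any safety laboratory variable. The only power figures are for efficacy responses. They identify the method: C4 in Table 1 of section 7.1 has SD 45.6, detectable difference 64.1 and n=9 per group. A two-sample t-test with noncentrality (64.1/45.6) × √(9/2) = 2.98 on 16 df has power 0.799, which matches the stated 80%. The same t-based framework is used below, for interval width only.

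**Inputs.**
- Arm size: 15 and 15, from the synopsis ("Sample size: 30 patients, 15 in placebo group, 15 in aldafermin treatment group").
- SD of total cholesterol between patients: 30 or 40 mg/dL. Assumed, not in the documents, and taken as equal at both visits.
- Correlation r between pre-dose and Visit 5 values: 0.3 to 0.9. Assumed, not in the documents.
- All 15 patients per arm have both panels. This is optimistic: accrual of 36 is there to replace very early withdrawals, and 7.2 counts as completed anyone dosed for more than one day, so a Visit 5 panel is not assured.

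**Formulas for the 95% CI half-width of the arm difference.** √(2/15) = 0.3651.
- Observed Visit 5 values: t(0.975, 28) × SD × 0.3651, with t = 2.048.
- Change from pre-dose: the same, multiplied by √(2(1−r)).
- ANCOVA on the pre-dose value: t(0.975, 27) × SD × √(1−r²) × 0.3651, with t = 2.052. This leaves out the small extra variance from chance baseline imbalance, so the ANCOVA figures are slightly favourable.

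Worked example at SD 40: observed values give 2.048 × 40 × 0.3651 = 29.9. ANCOVA at r=0.8 gives 2.052 × 40 × 0.6 × 0.3651 = 18.0.

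| r | SD 40: observed | SD 40: change | SD 40: ANCOVA | SD 30: observed | SD 30: change | SD 30: ANCOVA |
|---|---|---|---|---|---|---|
| 0.3 | 29.9 | 35.4 | 28.6 | 22.4 | 26.6 | 21.4 |
| 0.5 | 29.9 | 29.9 | 26.0 | 22.4 | 22.4 | 19.5 |
| 0.6 | 29.9 | 26.8 | 24.0 | 22.4 | 20.1 | 18.0 |
| 0.8 | 29.9 | 18.9 | 18.0 | 22.4 | 14.2 | 13.5 |
| 0.9 | 29.9 | 13.4 | 13.1 | 22.4 | 10.0 | 9.8 |

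(All in mg/dL.)

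The change score gains nothing at r=0.5 and is worse than observed values below that. ANCOVA is narrower at every r shown, but at r=0.3 the gain is too small to matter.

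**The class table.** Categories carry little information at this size. With 0/15 on placebo, a two-sided Fisher test gives p=0.10 for 4/15 and p=0.04 for 5/15 on aldafermin. No such test is planned; the figures only show how coarse the classification is. A shift table fixes what is being counted (new abnormalities) but is no less coarse, which is why a numeric baseline-adjusted difference is wanted beside it.

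**The case against.** The case on the other side is substantial, and most of it stands as a limit on how far the point goes.

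- **The plan is silent on change; it does not rule it out.** Pre-dose results are observed values too. If tables are produced by visit, which is not stated, the mean change per arm could be read off. True, but its variability and confidence interval could not.
- **Baseline is used for individual patients.** A reader might infer that the trial ignores baseline laboratory values altogether. The documents do not support that: clinically relevant changes become adverse events, are summarised, and clinically significant ones lead to a repeat test. These routes depend on judging one patient at a time and are not designed to show a moderate shift in an arm mean.
- **Observed-value comparisons are not biased.** A reader might infer that the safety table leans towards finding nothing. It does not: under randomisation the unadjusted arm difference is unbiased, and the loss is one of precision.
- **A rise within the normal range is not lost.** It leaves no mark in the three-way class, but it still moves the numeric summary.
- **The sizes rest on assumptions.** SD and r come from outside the documents, and no safety hypothesis test is planned. It therefore cannot be claimed that a lipid effect would probably be missed. Section 4.4 also attributes its list jointly to safety profile and mechanism; it does not predict a lipid rise.

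**Conclusion.** The point holds as a free improvement to the group-level safety summary. Section 7.2 and the synopsis state a specific method that uses no pre-dose value, while the trial plans paired panels and the protocol gives its own reason to look at lipids.

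The size depends on the unknown correlation. With 15 pairs per arm, the half-width for total cholesterol falls from about 30 mg/dL to about 29, 26, 24, 18 and 13 mg/dL at r=0.3, 0.5, 0.6, 0.8 and 0.9 (SD 40), and from about 22 to about 21, 19, 18, 13 and 10 mg/dL (SD 30). The gain is large if r is 0.8 or more and negligible near 0.3. These figures apply to ANCOVA, not to the simple change score, and describe precision only. The failure of the class table to separate abnormality at entry from new abnormality does not depend on any assumed number.

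**What to change.** In section 7.2 and the synopsis:

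1. Add, for laboratory tests, vital signs and ECGs, a summary by arm of change from the pre-dose value.
2. Add a shift table by arm, cross-classifying the pre-dose class with the Visit 5 class.
3. For total cholesterol, LDL, triglycerides and ALT, report the arm difference at Visit 5 from an ANCOVA on the pre-dose value of the same variable, with 95% CI, labelled descriptive.
4. State which pre-dose value is baseline (the Visit 1 or Visit 2 panel, whichever was drawn), and give the number of patients with both values.

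The cost is a few extra table columns and one degree of freedom per model. No new data, visits or patients are needed, and writing it down now avoids a post hoc choice of safety analysis.
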